## 5.5 Description of Study Process

1. **IDENTIFY PARTICIPANTS:** The research assistant will identify potentially eligible participants by looking through new patient and existing patient scheduling reports, as well as by accepting physician referrals. We are requesting a HIPAA waiver of authorization so that the research assistant may look in the Electronic Health Record to determine eligibility before approaching potentially eligible participants.
2. **CONSENT PARTICIPANTS:** The research assistant will approach the eligible participant either in-person or over the phone and introduce the study, answer any questions, and offer the potential participant time to think it over. If/When the potential participant decides to participate, the research assistant will obtain signed informed consent for participation in the research study. If the potential participant decides NOT to participate, the study team will not contact the person again. The caregiver will also be invited to participate; they will be given a study letter that contains the elements of informed consent.
3. **ADMINISTER BASELINE ASSESSMENT:** If the participant consents, the research assistant will administer the baseline assessment. For patients who are unable to complete the baseline assessment immediately following study consent (for example, if they are too fatigued or emotionally overwhelmed after their oncology consultation) the protocol will allow for participants to be randomized (see 4.0) and then complete the baseline survey (within two weeks of randomization). Questionnaire-based instruments will be administered 1) in person by a trained research assistant at the time of a routinely scheduled visit, 2) by e-survey, 3) by phone, 4) or by postal mail. Mode of collection will be recorded. The baseline assessment takes approximately 5 minutes to complete.
4. **RANDOMIZE PARTICIPANTS:** The research assistant will contact the central research assistant at Dana-Farber to randomize the participant:
  - A. For patients making a chemotherapy treatment decision at the time of study enrollment: After study consent and the baseline assessment, the study team will then randomize the patient to either the Usual IC Arm or the Investigational IC Arm of the study.
  - B. For patients NOT making a new chemotherapy treatment decision at the time of study enrollment (e.g. they are receiving ongoing treatment with first-line palliative chemotherapy), randomization will occur at the point at which the patient is faced with a new chemotherapy treatment decision (e.g. for cancer progression, or unacceptable treatment-related toxicity). After the patient's oncologist confirms that the patient is faced with a new chemotherapy treatment decision, the study team will then randomize the patient to either the Usual IC Arm or the Investigational IC Arm of the study.

**Title:** Improving Informed Consent for Palliative Chemotherapy: RCT of Usual IC versus Investigational IC

**Overall PI:** [name], Dana-Farber Cancer Institute

**Dana-Farber protocol version no./date:** v17 / August 30, 2017

Participants will be randomized 1:1 without blinding to receive either Usual Informed Consent or Investigational Informed Consent by utilizing a randomization algorithm managed by REDCap. This will be stratified according to whether the patient is 1st line palliative chemotherapy or 2nd line palliative chemotherapy.

5. **ADMINISTER INTERVENTION:** For patients randomized to the intervention, the research assistant or the patient's oncologist or primary nurse practitioner (depending upon oncologist preference) will give the participant the relevant interventional informed consent (IC) materials.

The treating oncologist will identify which chemotherapy regimen(s) are being considered, in order to select the appropriate IC tool(s) to give the patient. Although we anticipate that most oncologists will recommend a single treatment option and will request that patients be given a single IC video and companion booklet, patients may be given both IC tools if the oncologist has recommended consideration of either FOLFOX(+/-bevacizumab), FOLFIRI(+/-bevacizumab), FOLFIRINOX, Gemcitabine + nab-paclitaxel, or Gemcitabine.

The patient will be given the investigational IC tools after discussing his or her treatment options with the oncologist, baseline assessment and randomization. Patients will be given the intervention IC materials *as soon as possible* after discussing treatment recommendations with their oncologist but *prior* to their actual treatment decision and initiation. In select cases in which it is not possible to administer the intervention prior to the initiation of chemotherapy (e.g. such as a patient who opts to start a new chemotherapy regimen on the same day as their treatment discussion), it will be allowed to administer the intervention within 2 weeks of chemotherapy initiation. Every attempt will be made to ensure that the intervention is given to the patient as soon as feasibly possible, to ensure that the information is most relevant to them.

Research assistants (or the oncologist, or NP if they choose to distribute the intervention) will give participants randomized to the intervention a hard copy of the relevant investigational IC booklet(s), and will show the participant the investigational IC video on a pre-loaded study iPad. Patients will be offered a private area to review the video (such as consultation room, or in private during their chemotherapy infusion). Caregivers will be allowed to join in the viewing, if the patient prefers. If the patient wishes to watch the video during their chemotherapy infusion but no private room is available (e.g. they are receiving treatment in a semi-private infusion area), they will use headphones so as not to expose other patients to the intervention. All participants will be given the URL address and password to take with them so that they will be able to access the video at any time, and will be given a copy of the booklet to take home. The website will have capability of tracking the frequency with which the video is viewed.

In rare cases when administering the intervention in person is not possible, the research assistant will send the participant the IC booklet (which will also contain the web address and password for the IC video) via postal mail or electronic mail. The study research assistant will call the patient within one week to answer any questions about how to access the video.

In cases in which the study research assistant gives the participant the investigational IC booklet and video, research assistants will make it clear that their sole purpose is to orient the patient to the booklet/video and answer questions regarding how to access the video website and/or use the study iPad to watch the video. If the participant asks the study research assistant any question

**Title:** Improving Informed Consent for Palliative Chemotherapy: RCT of Usual IC versus Investigational IC

**Overall PI:** [name], Dana-Farber Cancer Institute

**Dana-Farber protocol version no./date:** v17 / August 30, 2017

about information presented in the investigational IC tools, the research assistant will refer the patient back to their primary oncologist, nurse practitioner, or infusion nurse.

6. **ADMINISTER POST-DECISION ASSESSMENT** within 0-4 weeks by the central research assistant at Dana-Farber after the day on which the participant made their treatment decision and initiated their new chemotherapy treatment. Questionnaire- based instruments will be administered 1) in person by a trained research assistant at the time of a routinely scheduled visit, 2) by e-survey, 3) by phone, 4) or by postal mail. Mode of collection will be recorded. The post-decision assessment takes approximately 20 minutes to complete.
7. **ADMINISTER FOLLOW-UP ASSESSMENT** within 2-3 months by the central research assistant at Dana-Farber after the day on which the participant made their treatment decision and initiated their new chemotherapy regimen. Questionnaire- based instruments will be administered to the participant and his/her caregiver 1) in person by a trained research assistant at the time of a routinely scheduled visit, 2) by e-survey, 3) by phone, 4) or by postal mail. Mode of collection will be recorded. The follow-up assessment takes approximately 20 minutes to complete.

**PATIENT:** Immediately following completion of the follow up assessment: Using methods similar to those described by White et al, the interviewer will show each participant his/her responses to the 2 questions about prognosis\*\*. Next, the interviewer will read the following standardized prompt: “Please take a moment to look at your responses. I notice that your answers to these two questions are [different/the same]. Can you tell me a little bit about this?”

The research assistant will then ask permission to audio-record the patient’s answers. If the participant is willing to answer the question but declines audio-recording, notes will be taken during and after the interview. The RA will use standard cognitive interviewing techniques, such as reflexive listening, “think alouds” and standard probes (“can you tell me what you mean by that?”) as necessary.

*\*\*Copy-pasted for reference - these are the 2 questions about prognosis:*

*Q: Based on what you have learned or been told, what is your understanding about how long the typical person with your type of cancer can expect to live?*

*A: 1, More than 10 years | 2, More than 5, but less than 10 years | 3, More than 3, but less than 5 years | 4, More than 2, but less than 3 years | 5, More than 1, but less than 2 years | 6, Less than 1 year*

*Q: Every person is different and every situation is unique. If you had to make a guess - based on what you have learned about your cancer, your cancer treatment, and what you know about yourself - how long do you think that you have to live?*

*A: 1, More than 10 years | 2, More than 5, but less than 10 years | 3, More than 3, but less than 5 years | 4, More than 2, but less than 3 years | 5, More than 1, but less than 2 years | 6, Less than 1 year*

**CAREGIVER:** Immediately following completion of the caregiver follow up assessment, the interviewer will read the following standardized prompt:

How do you think the person for whom you care would answer this question? Could you tell me a

**Title:** Improving Informed Consent for Palliative Chemotherapy: RCT of Usual IC versus Investigational IC

**Overall PI:** [name], Dana-Farber Cancer Institute

**Dana-Farber protocol version no./date:** v17 / August 30, 2017

little bit about why you answered in this way?

*Q: Based on what you have learned or been told, what is your understanding about how long the typical person with your type of cancer can expect to live?*

*A: 1, More than 10 years | 2, More than 5, but less than 10 years | 3, More than 3, but less than 5 years | 4, More than 2, but less than 3 years | 5, More than 1, but less than 2 years | 6, Less than 1 year*

How do you think the person for whom you care would answer this question? Could you tell me a little bit about why you answered in this way?

*Q: Every person is different and every situation is unique. If you had to make a guess - based on what you have learned about your cancer, your cancer treatment, and what you know about yourself - how long do you think that you have to live?*

*A: 1, More than 10 years | 2, More than 5, but less than 10 years | 3, More than 3, but less than 5 years | 4, More than 2, but less than 3 years | 5, More than 1, but less than 2 years | 6, Less than 1 year*

The research assistant will ask permission to audio-record the caregiver's answers. If the participant is willing to answer the question but declines audio-recording, notes will be taken during and after the interview. The RA will use standard cognitive interviewing techniques, such as reflexive listening, "think alouds" and standard probes ("can you tell me what you mean by that?") as necessary.

Once the participant completes the follow-up assessment, the research assistant will inform the participant that his/her study participation is now complete and will remunerate him/her with a \$25 gift card (this applies to patient and caregiver participants).

In order to ensure that all interviews are being done correctly, all research assistants will undergo training in qualitative and cognitive interviewing from the SSMC (survey and stats methodology core). The study team investigators ([name] and [name]) and a clinical social worker ([name]) will also conduct one-on-one training with all involved research assistants. This training will include a structural overview of the clinical teams involved with the care of GCC patients, and how to contact appropriate providers in a timely manner. Research assistants will be trained in how to recognize participant distress, assess its severity, and respond in an appropriate and compassionate manner. This training will include role plays modeling both mild, moderate and severe distress, with debriefing and feedback. The research assistant(s) will not implement this qualitative question until training in adverse reaction management has occurred.

The research assistant's first 3-5 cognitive interviews will be observed by a study investigator ([name]), who will offer post-interview debriefing and critiques. When RA has shown proficiency, RA would then conduct the qualitative interviews independently. A is the most appropriate person to conduct these interviews because patients/caregivers are already bringing up these issues exact within their interactions with her during the surveys.

**Title:** Improving Informed Consent for Palliative Chemotherapy: RCT of Usual IC versus Investigational IC

**Overall PI:** [name], Dana-Farber Cancer Institute

**Dana-Farber protocol version no./date:** v17 / August 30, 2017

The study team will also ensure that all interviews are being done correctly by having the study team investigator ([name]) listen to a sample of interview audio recordings (2 randomly selected recordings per month for each research assistant conducting interviews). Weekly team meetings will also be held so that the study investigator and research assistants have an opportunity to discuss any questions or concerns arising during the previous week's interview process. During these team meetings, potential interview situations will be discussed and mock interviews may be conducted. In addition, study team investigators and researchers conducting the interviews will be in regular communication to ensure that interviews are being conducted on-time and in the appropriate way.

**Title:** Improving Informed Consent for Palliative Chemotherapy: RCT of Usual IC versus Investigational IC

**Overall PI:** [name], Dana-Farber Cancer Institute

**Dana-Farber protocol version no./date:** v17 / August 30, 2017

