## 3.0 RESEARCH SUBJECT SELECTION

### Eligibility Criteria

#### Inclusion criteria:

- Diagnosis of metastatic colorectal cancer **OR** locally advanced pancreatic cancer **OR** metastatic pancreatic cancer **AND**
  - Is making a decision regarding treatment with 1st or 2nd line palliative chemotherapy. **OR**
  - Is receiving 1st line palliative chemotherapy, and is therefore likely to make a future decision about 2nd line chemotherapy (either for cancer progression or toxicity). This cohort of patients will be eligible for study enrollment and baseline assessment, but will not be subject to randomization until the time of their next treatment decision.
- Treating oncologist has recommended consideration of one or more of the regimens for which we have developed informed consent (IC) toolkits (FOLFOX, FOLFOX + bevacizumab, FOLFIRI, FOLFIRI + bevacizumab, FOLFIRINOX, Gemcitabine, or Gemcitabine + nab-paclitaxel).
  - Patients who are also considering treatment on a clinical trial are eligible, including those considering treatment on a clinical trial of FOLFOX (+/-bev) + investigational agent, or FOLFIRI (+/-bev) + investigational agent
- Age  $\geq$  21
- English proficient

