**Procedure for randomization (see schema on page 2):**

1. For patients making a chemotherapy treatment decision at the time of study enrollment: After study consent and the baseline assessment, the study team will then randomize the patient to either the Usual IC Arm or the Investigational IC Arm of the study using REDCap's 1:1 randomization algorithm, stratified by 1st-line or 2nd-line chemotherapy.
2. For patients NOT making a new chemotherapy treatment decision at the time of study enrollment (e.g., they are receiving ongoing treatment with first-line palliative chemotherapy), randomization will occur at the point at which the patient is faced with a new chemotherapy treatment decision (e.g., for cancer progression, or treatment-related toxicity). Research assistants will contact the treating oncologists prior to scheduled chemotherapy visits and/or restaging visits to remind them of their patient's participation on the study, and to request that the oncologist contact the research assistant in the event that a new treatment decision is being made. When the patient's oncologist confirms that the patient is faced with a new chemotherapy treatment decision, the study team will then randomize the patient to either the Usual IC Arm or the Investigational IC Arm of the study using REDCap's 1:1 randomization algorithm, stratified by 1st-line or 2nd-line chemotherapy. Patients who do not make a new treatment decision during the timeframe of this study will not be randomized, and will not complete future study assessments.

Participants will be randomized 1:1 without blinding to receive either Usual Informed Consent or Investigational Informed Consent by utilizing a randomization algorithm managed by REDCap. This will be stratified according to whether the patient is 1st line palliative chemotherapy or 2nd line palliative chemotherapy.

The name and telephone number of the research study person who will be responsible for registration and randomization is: [name], [[name]\\[contact]](mailto:[contact]), [contact].

When registering subjects, the study team will ask for the following information (see Appendix B):

- Name, telephone number, and email address of research assistant enrolling the participant
- Date subject signed informed consent

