- Subject and caregiver's phone numbers, emails, and postal mail addresses (reason for collecting these: so central research assistant at Dana-Farber can administer follow-up assessments)
- Subject and caregiver's ranks of preference regarding contact method
- Subject and caregiver's genders
- Subject and caregiver's initials
- Subject and caregiver's ages
- Subject ID number
- Primary oncologist
- Confirmation of eligibility
- Stratification or classification factors (1st versus 2nd line palliative chemotherapy)

**Procedure for assessment contact and reminders:** It is acceptable to administer each assessment aloud (via phone or in-person), via email (REDCap weblink), via iPad (REDCap), or via hard copy (in-person or postal mail). The baseline assessment will be administered immediately after the participant signs informed consent; the baseline caregiver assessment will be administered immediately after the caregiver receives the

**Title:** Improving Informed Consent for Palliative Chemotherapy: RCT of Usual IC versus Investigational IC

**Overall PI:** [name], Dana-Farber Cancer Institute

**Dana-Farber protocol version no./date:** v17 / August 30, 2017

study letter and agrees to participate. In rare cases when immediate administration is not possible, the central study research assistant at Dana-Farber will follow-up with the participant up to 3 times post-informed consent. One follow-up is defined as: an in-person approach OR a phone call with an accompanying email. If the participant is non- responsive after 3 attempts, then the study research assistant will mark the baseline assessment as missing and will not contact the participant about the baseline assessment again.

The post-decision assessment will be administered by the central study research assistant at Dana-Farber at any point between the day the participant starts chemotherapy and 4-weeks post-chemo start. During this 4 week period, the study research assistant will follow-up with the participant up to 3 times. One follow-up is defined as: an in-person approach OR a phone call with an accompanying email. If the participant is non- responsive after 3 attempts, then the study research assistant will mark the post-decision assessment as missing and will not contact the participant about the post-decision assessment again.

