#### **Instrument 1: Baseline Assessment (See Appendix C)**

The baseline assessment will assess socio-demographics, information/communication preferences, decision control preferences, and illness understanding. Patients will complete this assessment after consenting for the study, but before randomization. The baseline assessment takes approximately 5 minutes to complete.

**Title:** Improving Informed Consent for Palliative Chemotherapy: RCT of Usual IC versus Investigational IC

**Overall PI:** [name], Dana-Farber Cancer Institute

**Dana-Farber protocol version no./date:** v17 / August 30, 2017

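### Section 5.5 lets a deferred baseline survey follow unblinded randomization, contrary to Sections 4.0 and 5.2 and its own step 4A, which weakens the reference for the preferred-role outcome

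*Combined protocol and SAP*

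**What the plan says.** **Order of baseline and randomization.** Three places put the baseline first:

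- Section 5.2, Instrument 1: "Patients will complete this assessment after consenting for the study, but before randomization".
- Section 4.0, randomization procedure: "After study consent and the baseline assessment, the study team will then randomize the patient".
- Section 5.5, step 4A: "After study consent and the baseline assessment, the study team will then randomize the patient to either the Usual IC Arm".

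Step 3 of Section 5.5 makes an exception for patients too tired or upset after the consultation: "the protocol will allow for participants to be randomized (see 4.0) and then complete the baseline survey (within two weeks of randomization". Step 4 adds: "Participants will be randomized 1:1 without blinding".

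The assessment-contact procedure in Section 4.0 also foresees a delayed baseline ("In rare cases when immediate administration is not possible"), with up to three contacts and then a missing record. It mentions neither randomizing first nor a two-week limit.

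**Use of baseline answers.** The measures table in Section 5.4 lists the Control Preferences Scale at baseline only. The preferred-role outcome compares later reported involvement with that answer. Section 6.0 names this as a hypothesis under its Objective 2 and lists communication and decisional-control preferences among the exploratory moderators.

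**Tools and post-decision survey.** Sections 5.3 and 5.5 (step 5) normally give the tools before the treatment decision but, in selected cases, allow delivery up to two weeks after chemotherapy starts. Section 4.0 runs the post-decision survey from the day chemotherapy starts to four weeks later.

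**The concern.** A baseline measure should not depend on allocation. If a patient already knows the arm when asked how much control they want over decisions, the answer may reflect that knowledge. The comparison of preferred with actual role then has a reference taken after allocation, and so do the moderator analyses based on stated preferences. The direction of any shift is unknown. Sites following Section 4.0 or 5.2 would also act differently from sites following step 3, whose cross-reference to 4.0 leads to text without the exception.

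The second point concerns timing in the intervention arm only. A patient surveyed before late tools arrive gives post-decision answers that the tools could not have influenced. Treatment goal and risk understanding are measured at that survey alone, so an effect on them would be diluted.

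**Working it through.** **1. The plan's own figure.** Inputs from Section 6.0 (Power): 60% versus 40% inaccurate expectations, one-sided alpha 2.5%, power 80%. With pooled variance and no continuity correction:

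n per arm = [1.960 × √(2 × 0.5 × 0.5) + 0.8416 × √(0.6 × 0.4 + 0.4 × 0.6)]² / 0.20² = (1.386 + 0.583)² / 0.04 = 96.9, so 97 per arm and 194 in total.

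The stated 194 is reproduced. It concerns the primary outcome at the follow-up assessment, tested by Fisher's exact test with no baseline covariate. Nothing below changes it.

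**2. Baseline order, side by side.**

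| Place | Baseline before randomization? | Exception stated? |
|---|---|---|
| 4.0, randomization procedure | Yes | No |
| 4.0, assessment contact | Not ordered | Delay foreseen; no randomize-first rule, no two-week limit |
| 5.2, Instrument 1 | Yes | No |
| 5.5, step 3 | Normally | Yes, up to two weeks after randomization |
| 5.5, step 4A | Yes | No |
| 5.5, step 5 | Tools come after both | No |

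Step 3 therefore conflicts with three passages, and a fourth is incomplete. Step 5 keeps the tools after the baseline but does not say whether they wait for a deferred one.

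**3. Who is exposed.** Patients enrolled while on ongoing first-line treatment "will not be subject to randomization until the time of their next treatment decision"; step 4B repeats that "randomization will occur at the point at which the patient is faced with a new chemotherapy treatment decision". Their baseline is normally done at enrolment, so they are largely unaffected. The exposed group is patients who decide at enrolment and whose baseline is deferred. The documents give no frequency.

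**4. Tool and survey windows.** Late tools: days 0 to 14 after chemotherapy start. Post-decision survey: days 0 to 28. Overlap = 14/28 = 50% of the survey window. Delivery on day 14 leaves 28 − 14 = 14 days for the three permitted contacts. The primary assessment, at 2 to 3 months, lies beyond the overlap.

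**5. Illustration only; every input here is assumed.** If survey days are uniform over 0 to 28 and independent of delivery, the chance that the survey comes first is the mean delivery day divided by 28:

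- mean day 1: 1/28 = 3.6%
- mean day 3: 3/28 = 10.7%
- mean day 7: 7/28 = 25%

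If 5% to 20% of intervention patients receive the tools late, the share f surveyed first runs from 0.05 × 0.036 = 0.2% to 0.20 × 0.25 = 5%. If those patients answer as under usual consent, the observed effect is the true effect × (1 − f), so it shrinks by 0.2% to 5% of its size.

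**The case against.** The exception in step 3 is deliberate: it gives a reason and a time limit and stands directly before step 4A. A specific exception can fairly be read as qualifying the general rule beside it. That makes the mismatch partly editorial, but it does not restore a baseline taken without knowledge of the arm, and Sections 4.0 and 5.2 still say otherwise.

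On the tools, the text implies delivery first. Delivery is step 5 and the survey step 6, the investigational arm has its own post-decision form, and patients in that arm rate the tools' acceptability. The schema to which Section 5.3 refers for timing was not available. Section 6.0 also plans a description by self-reported exposure. These arguments stand and reduce this to a secondary point. They do not remove it: step 3 may itself follow step 4, so numbering does not bind. Use is also asked again at follow-up, so a patient surveyed before delivery may later report use. Only dates separate the cases.

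Four stronger readings are tempting, and the documents do not support them:

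- **Baseline after exposure to the tools.** Step 5 places the tools after the baseline. Only knowledge of the arm is at issue.
- **A fixed percentage bound per patient from 97 per arm.** That figure belongs to the follow-up power statement. Section 5.1 plans 244 patients, some may never be randomized, and surveys may be missing, so it is not the denominator for these secondary outcomes.
- **Dilution of satisfaction with consent materials.** A patient who has not received the tools cannot meaningfully rate them, so a missing answer is at least as likely as a diluted one.
- **Dilution of decisional conflict.** Late-tool patients have generally already decided, so later surveying would not recover such an effect.

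**Conclusion.** The contradiction over baseline timing is on the face of the text. Its consequence is limited to the preferred-role outcome and the exploratory moderators that use stated preferences. The frequency is unknown and the effect is probably small; this rests on the plan's description of delayed baselines as rare, not on a count. A reader might infer harm to the primary result. The documents do not support that, since the primary test uses no baseline answer and its time point is the follow-up assessment.

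The tool and survey windows overlap with no order in the supplied text. It cannot be concluded that the plan has no order, because the schema and forms may hold one. The outcomes open to dilution are mainly treatment goal and risk understanding. The 0.2% to 5% range is an illustration, not an estimate, and no loss of power is claimed. The change is optional but inexpensive.

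**What to change.** **Baseline.**

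- Reconcile the two procedures in Section 4.0, Instrument 1 in Section 5.2, and steps 3 and 4A of Section 5.5, so that all state the same rule and time limit.
- Where a baseline is deferred, collect it before the arm is disclosed where possible.
- Keep step 5's order (baseline, then tools) and do not carry the exception into it, since that could permit a baseline after exposure.
- Record the dates of randomization and baseline, and report how many baselines came second.
- Keep late baselines in the main analysis, and exclude them in a sensitivity analysis of the preferred-role and moderator results.

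**Post-decision survey.**

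- For late-delivery patients, schedule it after the tools are delivered, within the existing 0 to 4 week window. Permitted delivery timing stays as it is.
- Record delivery and survey dates, and report how many surveys came first.

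**Cost.** Amendment wording and a few date fields, some of which REDCap or the unseen forms may already hold. A few intervention patients are surveyed slightly later, with possibly some added non-response. Timing can be matched to the usual-consent arm only approximately, because late delivery exists in one arm.
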